5.3 LOST TO FOLLOW-UP

A subject will be considered lost to follow-up if he or she fails to return for 2 scheduled visits and is unable to be contacted by the study site staff.

The following actions must be taken if a subject fails to be available for a required study visit:

- The site will attempt to contact the subject and reschedule the missed visit and counsel the subject on the importance of maintaining the assigned visit schedule and ascertain if the subject wishes to and/or should continue in the study.
- Before a subject is deemed lost to follow-up, the investigator or designee will make every effort to regain contact with the subject (where possible, 3 telephone calls and, if necessary, a certified letter to the subject's last known mailing address or local equivalent methods). These contact attempts should be documented in the subject's medical record or study file.
- Should the subject continue to be unreachable, he or she will be considered to have withdrawn from the study with a primary reason of lost to follow-up.

6 STUDY ASSESSMENTS AND PROCEDURES

6.1 STUDY ASSESSMENTS

Participants will complete assessment at baseline and 2 months. Assessments will include interviewer-administered measures. Participants will also participate in a focus group for acceptability following completion of the intervention. Process measures for feasibility will be tracked throughout the study.

Acceptability, focus groups:

- assessment of intervention content
- perceived positive or negative effects
- appropriateness of intervention duration and frequency
- barriers to engagement, suggestions to improve the intervention
- overall satisfaction

Feasibility of the intervention using process measures:

- percentage of screened participants who are eligible
- percentage of eligible participants who enroll
- distribution of participants by demographics (age, race, ethnicity, gender)
- number of sessions attended
- participant adherence to study tasks
- overall study retention

Preliminary efficacy: baseline and 2-month follow-up:

- diabetes distress (Diabetes Distress Scale)
- diabetes self-management behaviors (Adherence to Refills and Medications scale, Summary of Diabetes Self-Care Activities)

- glycemic control (A1C test results from electronic medical records)

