1.2 SCHEDULE OF ACTIVITIES (SOA)

Activity	Activity Schedule
Mindfulness-Based Diabetes Education program sessions	Weeks 1 to 8: meet weekly
Study assessment visits – 2	1. Enrollment assessment visit
	2. 8-week assessment visit
Focus Group – 1	1. Focus group

INTRODUCTION

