2.2 END OF STUDY DEFINITION

Date of final visit for participant follow up assessment.

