3 STUDY POPULATION

3.1 INCLUSION CRITERIA

Inclusion criteria:

- age 19-64 years
- diagnosis of type 2 diabetes
- receipt of care at CGMHSA (one or more visits to primary care or diabetes clinic within the prior year)

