7.3 STATISTICAL ANALYSES

7.3.1 GENERAL APPROACH

Given our small sample size and the resultant lack of precision of an estimate of effect size, we will not estimate efficacy based on outcome measures. In addition, we will not be testing formal statistical hypotheses.

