7.3.2 ANALYSIS OF THE PRIMARY EFFICACY ENDPOINT(S)

Initial proposed analysis: To estimate effect size of the pilot intervention, we will perform paired t-tests to study the change in the primary outcome, A1C, and secondary outcomes, diabetes distress and diabetes self-management behaviors, from baseline to post-intervention. Analysis of covariance will be used to examine baseline to 2-month changes in primary and secondary outcomes while controlling for potential covariates of interest, such as demographics or disease severity. Distributions of continuous outcome variables will be examined for normality using box plots, stem and leaf plots, and normal probability plots. Variables that are determined to be non-normally distributed will be transformed or analyzed using non-parametric tests, such as Wilcoxon signed-rank test. All statistical tests will be two-sided using a significance level of 0.05. Statistical analysis will be completed using SAS, version 9.4 or later.

Analysis plan: We will generate descriptive statistics, including frequency distribution tables for categorical variables, as well as means, medians, standard deviations, and interquartile ranges for continuous variables, including diabetes distress.

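### Does the record-based A1C need a stated rule for which dated result counts as baseline and which as 2-month?

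*Combined protocol and SAP*

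**What the plan says.** Section 6.1 has a list headed "Preliminary efficacy: baseline and 2-month follow-up", and its last entry is "glycemic control (A1C test results from electronic medical records". The same section says "Assessments will include interviewer-administered measures" and names no laboratory test.

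Other sections bear on timing but do not fix it:

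- Section 1.2 lists the weekly sessions, an enrollment visit, an "8-week assessment visit" and a focus group. It shows no A1C draw and no date for pulling records.
- Section 2.2 defines the end of study as "Date of final visit for participant follow up assessment" and is silent on whether a later record result may be used.
- Section 3.1 requires "one or more visits to primary care or diabetes clinic within the prior year", which does not guarantee an A1C result.

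On analysis, 7.1 states that there is no formal hypothesis testing, and 7.3.1 adds "we will not estimate efficacy based on outcome measures". The analysis-plan paragraph of 7.3.2 asks for "means, medians, standard deviations, and interquartile ranges for continuous variables, including diabetes distress". A separate paragraph in 7.3.2, labelled as the initial proposal, calls A1C the primary outcome and describes paired t-tests. Section 7.2 gives a power calculation for the change in HbA1c.

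**The concern.** The questionnaires in the 6.1 list are dated by the visit at which they are given. A1C is the one listed efficacy measure whose date the study does not control. With no selection rule, two people extracting the same records could fill the table differently. One result could be entered at both times and look like no change. A result drawn after session 1 could be used as baseline. A participant with no result near week 8 could be left out or given a much later value. A reader of the table could not tell whether the two columns hold the same participants, whether the draws lie on either side of the program, or how far apart they are. If A1C change were the basis for a claim of efficacy, this would matter.

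**Working it through.** **The plan's own figure.** Inputs from 7.2: n = 30, SD of change 1.8%, two-sided paired t-test at 0.05. The noncentrality is δ√n/SD. At δ = 1.0% it is 1.0 × 5.477/1.8 = 3.04, and with 29 degrees of freedom power is 83.7%. Power of 80% is reached at δ = 0.953%, which rounds to the stated 1.0%. The figure reproduces, and it assumes 30 complete pairs.

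**How often one result could serve twice.** The documents give neither the testing frequency nor the time from enrollment to session 1. Assume tests every k weeks at random phase, session 1 at week 0, the final visit at week 8, and enrollment g weeks before session 1. Assume also that the extractor takes the result nearest each visit, which is not in the plan. One draw is nearest both visits with probability max(0, 1 − (8 + g)/k):

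| k (weeks) | g = 0 | g = 2 | g = 4 |
|---|---|---|---|
| 8 | 0 | 0 | 0 |
| 13 | 5/13 = 38% | 3/13 = 23% | 1/13 = 8% |
| 26 | 18/26 = 69% | 16/26 = 62% | 14/26 = 54% |

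At k = 13 this is 11.5, 6.9 or 2.3 of 30 participants. The draw nearest enrollment falls after session 1 with probability max(0, (k/2 − g)/k). At k = 13 that is 50%, 35% or 19%.

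The range runs from none to about two thirds. It follows from the assumed rule and the assumed testing interval. A clinic draw arranged near a visit is not excluded and would break the random-phase model.

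**What a simple rule would achieve.** Take the natural rule: baseline is the latest result on or before session 1, and 2-month is the result after session 1 closest to week 8. Suppose, for illustration, that a fall in A1C builds linearly to week 8 and then stays flat. Let u be the week of the first draw after session 1.

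- k = 13, records pulled late: for u below 1.5 the next draw, at u + 13, is closer to week 8 and shows the full fall. For u from 1.5 to 8 the share shown is u/8. For u above 8 it is 1. The mean is [1.5 + (64 − 2.25)/16 + 5]/13 = 0.80, and every participant has a value.
- k = 13, records pulled at week 8: only u up to 8 counts. A value exists for 8/13 = 62%, with mean share 0.50.
- k = 8: by the same steps, 0.875 with late extraction and 0.50 at week 8.

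So a selection rule without an extraction cut-off still lets the 2-month figure depend on when the record is pulled. With late extraction, (4 − 1.5)/13 = 19% of 2-month values at k = 13 are drawn before week 4. At k = 26, (26 − 16)/26 = 38% are drawn more than 8 weeks after the visit.

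**What the result feeds.** Under 7.1, 7.3.1 and the analysis-plan paragraph of 7.3.2, A1C enters no test and no efficacy estimate. That paragraph asks for summaries of continuous variables, names only diabetes distress, and specifies no change score. A zero change from double use needs a within-person change analysis, which appears only in the paragraph labelled as the initial proposal.

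**The case for a change.** The strongest reply is that the gap reaches beyond a descriptive table. A1C is called the primary outcome in 7.3.2, it is the sole basis of the power calculation in 7.2, and 1.1 lists preliminary efficacy among the endpoints. If 3, 6, 9 or 15 of 30 participants (an assumed range) lacked a second result and were left out, power at a 1.0% change would fall from 83.7% to 79.4%, 74.1%, 67.8% or 51.7%. If one result were used twice for them, a true mean change of 1.0% would be recorded as 0.9%, 0.8%, 0.7% or 0.5%. Fixing the rule before extraction would also prevent dates being chosen after values are seen, at the cost of a few sentences.

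The arithmetic stands, but its relevance does not. The power losses belong to a t-test that 7.1 and 7.3.1 set aside. The primary-outcome label sits in the initial-proposal paragraph. Whether that paragraph and 7.2 fit with 7.3.1 is a separate question from record dating. A descriptive mean does still need a defined value at each time, and that part of the objection holds. It is met by ordinary extraction practice: one dated result per column, missing if there is none, and the count reported. The SOPs, case report forms and source worksheets mentioned in 8.1.4 and 8.1.5.1 might also hold abstraction rules. They are not available here, and the conclusion does not rely on them.

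**Conclusion.** The omission is real, but it is missing detail rather than an error, and no change to the plan follows. No stated rule gives a wrong result. The effect is confined to how one descriptive summary is read, and the acceptability and feasibility conclusions stand whichever reasonable dating is used. The documents cannot show how many participants would lack a 2-month value or have one result used twice: 0% to 69% double use rests on a nearest-result rule and testing intervals that the plan does not contain. A short selection rule would tidy the table. Without an extraction cut-off it would leave much of the variation in place (a share of 0.50 against 0.80 at assumed 13-week testing), and even with one it would not make record values into an 8-week change. This conclusion assumes that 7.3.1 and the analysis-plan paragraph of 7.3.2 govern. It would not carry over if A1C change were used to claim an effect.

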6.2 ADVERSE EVENTS AND SERIOUS ADVERSE EVENTS

6.2.1 DEFINITION OF ADVERSE EVENTS (AE)

Adverse event means any untoward medical occurrence associated with the use of an intervention in humans, whether or not considered intervention-related (21 CFR 312.32 (a)).

6.2.2 DEFINITION OF SERIOUS ADVERSE EVENTS (SAE)

An adverse event (AE) is considered “serious” if, in the view of either the investigator or sponsor, it results in any of the following outcomes:

- Death
- A life-threatening adverse event (of note, the term “life-threatening” refers to an event in which the subject was at risk of death at the time of the event, rather than to an event which hypothetically might have caused death if it were more severe)
- inpatient hospitalization or prolongation of existing hospitalization
- a persistent or significant incapacity or substantial disruption of the ability to conduct normal life functions
- or a congenital anomaly/birth defect.

Important medical events that may not result in death, be life-threatening, or require hospitalization may be considered serious when, based upon appropriate medical judgment, they may jeopardize the subject and may require medical or surgical intervention to prevent one of the outcomes listed in this definition. Examples of such medical events include allergic bronchospasm requiring intensive treatment in an emergency room or at home, blood dyscrasias or convulsions that do not result in inpatient hospitalization, or the development of drug dependency or drug abuse.

6.2.3 CLASSIFICATION OF AN ADVERSE EVENT

6.2.3.1 SEVERITY OF EVENT

For adverse events (AEs), the following guidelines will be used to describe severity:

- **Mild** – Events require minimal or no treatment and do not interfere with the subject’s daily activities.
- **Moderate** – Events result in a low level of inconvenience or concern with the therapeutic measures. Moderate events may cause some interference with functioning.
- **Severe** – Events interrupt a subject’s usual daily activity and may require systemic drug therapy or other treatment. Severe events are usually potentially life-threatening or incapacitating. Of note, the term “severe” does not necessarily equate to “serious.”

6.2.3.2 RELATIONSHIP TO STUDY INTERVENTION

All adverse events (AEs) must have their relationship to study intervention assessed by the clinician who examines and evaluates the subject based on temporal relationship and his/her clinical judgment. The degree of certainty about causality will be graded using the categories below. In a clinical trial, the study product must always be suspect.

- **Related** – The AE is known to occur with the study intervention, there is a reasonable possibility that the study intervention caused the AE, or there is a temporal relationship between the study intervention and event. Reasonable possibility means that there is evidence to suggest a causal relationship between the study intervention and the AE.
- **Not Related** – There is not a reasonable possibility that the administration of the study intervention caused the event, there is no temporal relationship between the study intervention and event onset, or an alternate etiology has been established.

6.2.3.3 EXPECTEDNESS

The Principal Investigator will be responsible for determining whether an adverse event (AE) is expected or unexpected. An AE will be considered unexpected if the nature, severity, or frequency of the event is not consistent with the risk information previously described for the study intervention.

6.2.4 TIME PERIOD AND FREQUENCY FOR EVENT ASSESSMENT AND FOLLOW-UP

The occurrence of an adverse event (AE) or serious adverse event (SAE) may come to the attention of study personnel during study visits and interviews of a study subject presenting for medical care, or upon review by a study monitor.

All AEs including local and systemic reactions not meeting the criteria for SAEs will be captured on the appropriate case report form (CRF). Information to be collected includes event description, time of onset, clinician's assessment of severity, relationship to study product (assessed only by those with the training and authority to make a diagnosis), and time of resolution/stabilization of the event. All AEs occurring while on study must be documented appropriately regardless of relationship. All AEs will be followed to adequate resolution.

Any medical condition that is present at the time that the subject is screened will be considered as baseline and not reported as an AE. However, if the study subject's condition deteriorates at any time during the study, it will be recorded as an AE.

Changes in the severity of an AE will be documented to allow an assessment of the duration of the event at each level of severity to be performed. AEs characterized as intermittent require documentation of onset and duration of each episode.

The Study Coordinator will record all reportable events with start dates occurring any time after informed consent is obtained until 7 (for non-serious AEs) or 30 days (for SAEs) after the last day of study participation. At each study visit, the Study Coordinator will inquire about the occurrence of AE/SAEs since the last visit. Events will be followed for outcome information until resolution or stabilization.

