Emotional Distress. Participants will complete the 17-item DDS measure after informed consent is obtained, which will be scored by study personnel to determine eligibility. Additionally, measures of emotional distress will be assessed at baseline and 2-month follow-up for intervention participants. The measures assess the level of diabetes distress and depressive symptoms that a participant is experiencing, these are not diagnostic tests. Our study measures will not ask about suicidality. Participants may experience emotional distress related to participating in the intervention, due to the focus on emotional distress. Participants will be informed that they may stop participation at any time if they feel uncomfortable. Additionally, if a participant appears to be in emotional distress, study staff will inquire as to the participant's well-being and whether they wish to stop the study visit or session. Participants who disclose potentially harmful information (e.g., suicidality) will be immediately referred for an assessment by behavioral health at CGMHSA. All participants will be provided with a letter outlining services that details information on available mental health services at CGMHSA and low-cost resources available in Jefferson County.

Inconvenience. Participating in the study may inconvenience patients because of the time needed to collect data and participate in the intervention sessions.

Alternative Treatments and Procedures: All study participants, including those in the single-arm pilot intervention, will have full access to all available standard of care clinical services at CGMHSA, and are permitted to withdraw or refuse participation at any time.

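### Adverse events are actively asked about only at study visits, so no inquiry is prescribed for participants who stop attending or within the 7/30-day recording window

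*Combined protocol and SAP*

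**What the plan says.** All references are to the combined protocol and SAP.

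- **Completeness (6.2.4).** Every adverse event during the study is to be documented whatever its cause, with changes in severity and the onset and duration of each intermittent episode.
- **Window (6.2.4).** Events are recorded from consent "until 7 (for non-serious AEs) or 30 days (for SAEs) after the last day of study participation".
- **Active inquiry (6.2.4).** "At each study visit, the Study Coordinator will inquire about the occurrence of AE/SAEs since the last visit".
- **Other routes (6.2.4).** Events may also come to light when a participant presents for care, or when a monitor reviews the study.
- **Schedule (1.2).** One row reads "Study assessment visits – 2": enrollment and the "8-week assessment visit". The program sessions have their own row, "Weeks 1 to 8: meet weekly", and the focus group a third.
- **Wording (1.5.1).** If a participant seems distressed, staff ask "whether they wish to stop the study visit or session".
- **End of study (2.2).** "Date of final visit for participant follow up assessment".
- **Missed visits (5.3).** Loss to follow-up is declared after two missed visits and failed contact. Before that, staff try up to three calls and, if needed, a letter.
- **Safety analysis (7.3.4).** Frequency tables are planned. No denominator is named.

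**The concern.** The recording requirement is broader than the method given to meet it. If *study visit* means an assessment visit, the coordinator asks once after baseline, about the preceding eight weeks. A single recall question of that length is a weak source for the onset and duration of intermittent events. A participant who misses that visit is not actively asked at all. The 7-day and 30-day periods come after participation has ended, and nothing says how staff learn of events in them.

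The matter is not trivial for this intervention. Section 1.5.1 names emotional distress from the program as a risk and tells participants they may stop if uncomfortable. Section 5.1 lists adverse effects first among the reasons for stopping the study. Both depend on events being found. A low count in the 7.3.4 table could not be read without knowing how many people were asked.

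**Working it through.** The plan gives no figure on this point to reproduce. The check is a count of contacts, followed by an illustration.

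**1. What counts as a visit.** For the narrow reading (assessment visits only): 1.2 lists sessions and assessment visits on separate rows; 1.5.1 names the visit and the session as alternatives; and 6.2.4 gives the inquiry to the coordinator, while 4.1.1 has the principal investigator deliver the sessions and no section places the coordinator there. For the broad reading: 5.3 requires two missed visits, and with one assessment visit after baseline that rule works only if sessions can be visits. The narrow reading has more support, but the term is ambiguous.

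**2. Contacts from week 1 on.** 8 sessions + 1 assessment + 1 focus group = 10. An inquiry is prescribed at 1 of them on the narrow reading, and at 8 + 1 = 9 if sessions count.

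**3. Participants who stop attending.** Narrow reading: anyone who misses week 8 is not asked. Broad reading: they are asked up to the last session attended, and not after. The calls and letter in 5.3 are for rescheduling and retention; no adverse-event question is attached.

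**4. The 7/30-day window.** The number of contacts dated within it is 0. The focus group comes after the intervention (2.1, 6.1) but has no date, and its stated purpose is acceptability. If it counts as participation, the window opens after it. If it does not, it may fall inside the window, but no adverse-event inquiry is assigned to it.

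Share of the recording period after participation, taking consent as day 0 and day 56 (8 × 7) as the last day (assumption), is w/(56 + w):
- non-serious: 7/63 = 11%
- serious: 30/86 = 35%

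A longer gap between consent and week 8 would lower both shares.

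**5. Illustration of size (narrow reading).** N = 30 is the maximum in 4.1.1. Dropout is not given, because retention is itself an outcome (6.1), so 0 to 40% before week 8 is assumed. With m participants asked:
- one-sided 95% upper bound for zero events: 1 − 0.05^(1/m)
- apparent frequency over 30 when the true risk is 10%: 0.10 × m/30. This takes the same risk in dropouts and no dropout event found by another route.

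| Assumed dropout | m asked | Upper bound, zero events | Apparent frequency, true risk 10% |
|---|---|---|---|
| 0% | 30 | 9.5% | 10% |
| 10% | 27 | 10.5% | 9% |
| 20% | 24 | 11.7% | 8% |
| 30% | 21 | 13.3% | 7% |
| 40% | 18 | 15.3% | 6% |

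Using 30 as the denominator gives a bound of 9.5% in every row.

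**The case against.** The best reply is that events have several ways of surfacing. Section 6.2.4 names presentation for care and monitor review. Participants receive care at the recruiting health system (3.1). A physician meets them weekly (4.1.1), and staff check on anyone who looks distressed (1.5.1). The focus group covers negative as well as positive effects as participants see them (6.1), and missed visits trigger calls (5.3). The 7/30-day clause says which events must be recorded; it does not promise a contact. This is also a small single-arm pilot with no formal safety rate.

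Much of this stands, and it limits the point:

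- A reader might infer that events in dropouts and after week 8 will be missed, or that the window is empty by design. The documents do not support that. Passive routes exist, and events learned of by any route are recorded.
- A reader might infer that the safety table claims full coverage. Section 7.3.4 makes no such claim and states no rate or bound. The completeness wording is in 6.2.4.
- A reader might suppose that distressed participants are the ones most likely to leave. The documents do not say so; they say only that distress is a risk and that leaving is allowed.

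What does not stand is that these routes close the gap. The well-being check needs attendance and visible distress. The calls carry no adverse-event question. Distress that never reaches a clinic is unlikely to appear in records. Counting sessions as visits helps those who attend, but not those who have stopped, and it adds no contact after week 8.

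**Conclusion.** The point holds as a gap in ascertainment. Active inquiry is tied to an undefined term that most likely gives one inquiry after baseline. On either reading, none is prescribed for participants who stop attending, and no adverse-event contact is scheduled in the 7/30-day window. The stated method therefore cannot assure the documentation that 6.2.4 requires, and events in those places are at risk of under-ascertainment.

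The size cannot be fixed from the documents. Across the assumed dropout range, the bound for zero events moves from 9.5% to at most 15.3%; at 20% dropout the difference is 11.7 − 9.5 = 2.2 percentage points. No planned decision uses such a bound. The case for change rests on the mismatch between requirement and method, which does not depend on those figures, and on the low cost of repair. It is a worthwhile correction, not a threat to the pilot's feasibility or acceptability aims.

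**What to change.** In 6.2.4:

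1. State that existing staff, identified by role, ask the adverse-event question at each weekly session, privately and one to one, and at the week-8 visit. Say whether the focus group counts as a visit for this purpose.
2. Add the same question to the missed-visit calls already planned in 5.3.
3. Define the last day of participation, including for those who withdraw. Then either close the 7/30-day window with a check of the medical record already used for A1C (6.1), made after the window has ended, or restate the window to end at the last scheduled contact.

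In 7.3.4, report how many participants were asked, beside the event counts.

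The cost is a few minutes of private staff time per participant at each session, one record look-up each, and more minor events recorded. Privacy is a real constraint: sessions are groups of 5 to 10, and 1.5.1 names breach of confidentiality as the main risk, so the question should not be put to the group. The record check finds only events that reached the health system, which is a reason to keep the direct questions as well.
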